Rationale: In severe COPD, breathlessness is a distressing symptom which has a huge impact on quality of life. Management of breathlessness is complex and should comprise both pharmacological and non-pharmacological interventions, tailored to the individual needs of the patient and provided by a multidisciplinary team. Such 'breathlessness services' have been developed in recent years, mainly in the United Kingdom. In the Netherlands, these services do not yet exist in primary or secondary care.

Objectives:

To assess feasibility of a Dutch breathlessness service, and to evaluate patient satisfaction.

Study design: Single-centre, non-blinded mixed-methods, cohort feasibility study.

Study population: Patients with COPD (diagnosed by a pulmonologist,

postbronchodilatator FEV1/FVC below the lower limit of normal) and refractory dyspnea

(troubled by breathlessness in spite of optimization of COPD treatment) who are able to visit

the outpatient clinic.

Intervention:

The intervention will be delivered by a multidisciplinary team, formed by a pulmonologist, a physiotherapist with expertise in COPD, and 3 respiratory nurses. For every patient, an individual management plan will be developed, based on the Breathing Thinking Functioning-model (see main document for details). The main intervention is delivered by both the respiratory nurse and the physiotherapist, twice a week for two to six weeks. During these sessions, patients learn strategies to cope with their dyspnea in both a cognitive and functional manner. The pulmonologist will prescribe opioids and/or benzodiazepines if applicable.

Main study parameters/endpoints:

Feasibility: 75% of patients fullfills intervention

Nature and extent of the burden and risks associated with participation, benefit and group relatedness:

The only burden for participants will be the hospital visits. However, these visits will be minimised as much as possible by combining them with other hospital visits where possible. If visiting the hospital is too burdensome, home visits will be arranged.

1. INTRODUCTION AND RATIONALE

Chronic Obstructive Pulmonary Disease (COPD) is a progressive disease causing about 7000 deaths in the Netherlands each year, thereby being the fourth leading cause of death (1). Studies have shown a high symptom burden in patients with end-stage COPD, at least similar to patients with incurable lung cancer (2). The main symptom is dyspnea, or breathlessness, which increases as disease progresses. It often results in emergency hospital admissions, which results in a high burden of disease on both patient, relatives and the health care system. Patients with COPD who experience refractory symptoms may be referred to a tertiary rehabilitation centre, where adequate patient education is provided including help with breathlessness, in an inpatient setting. However, patients with advanced respiratory failure are not always eligible for such programmes due to their instability, or they do not wish to be away from home for such a long period of time. Those patients are mostly dependent on their physiotherapist for breathlessness management. However, dyspnea is a complex symptom with cognitive and behavioural aspects. Most physiotherapists are not trained to address breathlessness in its full complexity.

In recent years, Booth and Spathis have developed the breathing-thinking-functioning model (BTF), which conceptualizes the three cognitive and behavioural reactions to dyspnea (3).

Breathing domain: Dyspnea causes dysfunctional breathing patterns with an increased respiratory rate and use of accessory muscles, leading to inefficient (dead space) ventilation. Furthermore, patients with COPD who feel breathless tend to focus on the in-breath instead of on the out-breath. This promotes dynamic hyperinflation which increases the breathlessness and the work of breathing. When addressing the breathing domain, patients learn adequate breathing techniques. Also, they will be given a hand-held fan. Growing evidence suggests that cool airflow from a fan can decrease breathlessness (13).

Thinking domain: misconceptions such as 'I will suffocate', but also memories of earlier episodes of dyspnea, lead to anxiety and distress in many patients. This leads to tachypnea which increases dyspnea. When addressing the thinking domain, patients learn that they may feel very breathless but will not suffocate. Also, they will learn how inadequate breathing techniques caused by anxiety influence their complaints.

Functioning domain: Many breathless patients avoid physical activity. This leads to both isolation and deconditioning, which supports the vicious circle of dyspnea. When addressing this domain, patients learn that it is vital to stay as active as possible, and that it may be harmful to always avoid exercise. Also, they learn how to divide their limited energy and to avoid exhaustion.

The intervention that will be investigated in this study is called Ademen Denken Doen (ADD). ADD is a Dutch version of BTF, adjusted to the health care situation in the Netherlands. There are two noteworthy differences between ADD and breathlessness services that have previously been investigated in other countries (mostly the UK and Germany) (6,7,8,9,10):

The first difference concerns participating health care professionals. In existing breathlessness services, palliative care teams have a leading role, including occupational

Introductiondyspneaserviceversie4

therapists. The Dutch situation is different since in most hospitals, palliative care is only available as an inpatient service. In the Netherlands, respiratory nurses and physiotherapists play an important role in supporting patients with COPD. Therefore, for this study we will set up an ADD training for respiratory nurses and physiotherapists. In the future, we aim to make the intervention applicable to physiotherapists and respiratory nurses outside our own hospital.

The second difference between existing dyspnea services and ADD concerns the targeted population. ADD is set up primarily for patients with COPD. Existing dyspnea services are not disease-orientated but symptom-orientated, and treat all patients with refractory dyspnea. The main reason for our focus on COPD is that ADD is set up by a pulmonology department instead of a palliative care team. The majority of dyspnoic patients that we see suffer from COPD. As mentioned before, this is a large patient category with a high burden of disease who frequently have unmet needs, which justifies our choice to focus on COPD for this pilot. Furthermore, the etiology of dyspnea is different in COPD from dyspnea in heart failure, cancer or pulmonary fibrosis. COPD leads to dynamic hyperinflation, which is worsened by rapid shallow breathing – a pattern of breathing promoted by anxiety (11). Anxiety is highly prevalent in COPD (12), probably due to its unpredictable course and due to the dyspnea itself. Many patients with COPD report fear of suffocation. Both the dysfunctional breathing pattern and the irrational fears elicited by breathlessness, are key elements of BTF/ADD. We therefore assume that specifically patients with COPD have even more to gain from ADD than patients with other casues of dyspnea. Nevertheless, if this intervention is effective, in the future the service should be made available to other patient groups.

Our goal is to use this feasibility study as a pilot study for a phase III randomised controlled clinical trial, in which effectiveness of ADD will be tested in several Dutch hospitals. In this phase III study, effectiveness will be measured using the CRQ (Chronic Respiratory Disease Questionnaire), domain of mastery. Therefore, we also measure CRQ in this feasibility trial at baseline and after the intervention. If no effect on CRQ is measured in this trial, we need to consider whether the intervention should be adjusted before we set up a phase III trial. However, due to the design of this trial, effectiveness of the intervention cannot be assessed.

2. OBJECTIVES

Primary objective:

to assess feasibility of ADD. Pre-defined criteria for feasibility is: 75 percent of included patients complete the intervention. Based on previous research on dyspnea services, we made the assumption that it is not realistic to expect a higher percentage of completion, since this is an elderly patient population with multimorbidity. Patients who quit the intervention because of a COPD exacerbation are replaced by another participant; however patients may drop out of the intervention for different reasons: because they do not want extra hospital visits, because they do not find the intervention helpful, because of family circumstances or because they have other medical complaints.

Secondary objectives:

- 1. To describe the components and practical aspects of ADD. These will be described in each patients CRF. Off note, ADD is an intervention that is different for each patient: depending on the most important component for them (breathing/thinking/functioning) and how many sessions they need to learn to control their breathlessness. Therefore we describe the number of sessions in each CRF.
- 2. To evaluate patiens' experiences with ADD, assessed with semi-structured interviews with patients and carers after 6 weeks.

3. STUDY DESIGN

The intervention will be delivered by a multidisciplinary team, formed by a pulmonologist, a physiotherapist with expertise in COPD, and 3 respiratory nurses.

Prior to start of the study, physiotherapist and respiratory nurses receive ADD training by pulmonologist, who has received an BTF training in Cambridge.

Step 1: All pulmonologists, residents and respiratory nurses of the Spaarne Gasthuis recruit patients with COPD with refractory breathlessness who fullfill the inclusion critera (see chapter 4).

Step 2: Patients who are eligible are given an information letter by the recruiting health care professional, or the letter is sent to the patient by a member of the ADD team. After at least 7 days, they receive a call from a member of the ADD team, asking if they have any questions concerning the study and whether they want to participate.

Step 3: Assessment for eligibility by pulmonologist (if not eligible, this is noted in case record form); first appointment within one week.

Step 4: First appointment (approximately 1.5 hrs). Patient comes with key (informal) carer.

- Explanation of ADD by pulmonologist and nurse.
- Patient signs informed consent form
- Aided by nurse, patient fills in the CRQ.
- Informal caregiver gives NRS rating for distress due to patient's breathlessness
- Patient meets physiotherapist
- Current medication is reviewed by pulmonologist. Medication for symptom control is optimised if necessary (e.g., morphine for dyspnea).
- Patient receives ADD booklet with breathing exercises and relaxation exercises and a handheld fan, and explanation why this works (stimulation of the nervus vagus in the face)

Step 5: At the end of the first appointment, the customized intervention program is made together with the patient.

- 1. All patients will have at least one session with the physiotherapist. The maximum number of sessions is six (once every week).
- 2. All patients will have weekly contact with the respiratory nurse; at least two times in the hospital (combined with physiotherapist), other contacts may be by telephone. If it is too burdensome for patients to come to the hospital, they will receive a home visit. During these contacts, the nurse will go through the given information again, coach the patient, and assess whether the intervention is helpful for the patient.

Table 1)

	explanation	intervention	Intervention is given by
Breathing	Dysfunctional breathing	Breathing retraining directions	Physiotherapist
	pattern	(relaxed tummy breathing, huffing	pulmonologist
	(too shallow, too quick, not	exercises, pursed lip breathing,	(medication)
	enough time to breath out)	reduce respiratory rate, focus on	Nurse (crisis plan)
		the breath out, recovery	
		breathing)	
		Relaxation technique	
		Find comfortable position	
		Breathing round a rectangle	
		Medication (when to take what)	
		Handheld fan with explanation	
		Crisis plan for exacerbation	
Thinking	Too much focus on breathing Fear of suffocating Traumatic past experiences Distress, anxiety	Explanation: Patients with COPD do not suffocate Episodes of breathlessness will usually stop within 20 minutes Offer anxiety management strategies Offer mindfulness, relaxation (change (shoulder) position Patient specific action plan	Nurse
Functioning	Breathless people avoid activity, which leads to deconditioning	Individualized exercise plan Energy conservation strategies ("pacing" instead of all/nothing pattern) Advise on posture/planning/prioritising Advise on breathing technique during exercise (blow as you go, push things rather than pull them) Advise on nutrition Sleep hygiene assessment whether mobility aids are indicated	Nurse Physiotherapist

Introductiondyspneaserviceversie4

Step 6: After the six week study period, patient comes for the final visit together with informal caregiver.

- Aided by nurse, patient fills in the CRQ
- Informal caregiver gives NRS rating for distress due to patient's breathlessness
- Member of ADD team conducts a semi-structured interview with both patient and informal caregiver to explore their experiences with ADD.

Step 7: After the last patient has fulfilled the intervention, the ADD team undergoes a structured interview regarding the intervention.

Main study parameters/endpoints:

Primary endpoint: Feasibility: 75% of included patients fullfills the intervention.

Secondary endpoints:

- 1. To describe the components and practical aspects of ADD. These will be described in each patients CRF. Off note, ADD is an intervention that is different for each patient: depending on the most important component for them (breathing/thinking/functioning) and how many sessions they need to learn to control their breathlessness. Therefore we describe the number of sessions in each CRF.
- 2. To evaluate patiens' experiences with ADD, assessed with semi-structured interviews with patients and carers after 6 weeks.

4. STUDY POPULATION

Inclusion criteria

Base population: COPD patients who are treated in the outpatient clinic of the Spaarne Gasthuis.

In order to be eligible to participate in this study, a patient must meet all of the following criteria:

- COPD, diagnosed by a pulmonologist, with postbronchodilatator FEV1/FVC below the lower limit of normal
- refractory dyspnea (troubled by breathlessness in spite of optimization of COPD treatment, MRC dyspnea score at least 2 points). Since dyspnea is a symptom, there are no objective criteria, only questionnaires. As in other studies investigating dyspnea services and pulmonary rehabilitation, we use the MRC score for inclusion, which scores during which activity the patient becomes dyspnoic. A MRC dyspnea score of 2 points indicates dyspnea during hurrying or walking up a slight hill. Off note, this intervention is only offered to patients who complain of dyspnea in their daily life. Many COPD patients have an MRC dyspnea score of 2, but are not troubled by the symptom.
- able to visit the outpatient clinic
- able to read and understand the Dutch language
- mentally competent, as assessed by recruiting health care professional

Exclusion criteria

A potential patient who meets any of the following criteria will be excluded from participation in this study:

- An acute exacerbation of COPD, leading to hospitalisation, in 6 weeks before inclusion.
- An acute exacerbation during the study period, will lead to exclusion with the
 possibility to re-enter after stabilization. In that case, patients will follow the same
 study procedures again.
- Active participation in another trial

Sample size calculation

Number of subjects: 20.

Rationale: The primary aim of the present study is to assess feasibility of a new service in the Netherlands. This service is an adjusted variant of an existing service for which there is robust evidence. If ADD is feasible and effective in a pilot study population, we aim to conduct a larger randomised clinical trial regarding effectiveness. In that case, our power

C1onderzoeksprotocol2019.199versie4 dd 01-082019

Introductiondyspneaserviceversie4

calculation would be comparable to the study by Higginson et al. (9) When using the Chronic Respiratory Disease Questionnaire mastery domain as primary outcome, they calculated that more than 34 patients per group would detect a mean difference of 0·70 (SD 1), a p value of less than 0·05 at power 80%. To allow for a conservative estimated attrition of 40% they planned to recruit at least 110 patients into their study. Since it is a rule of thumb that a pilot study includes at least 10% of subjects for the full study, we would need at least 11 patients for this pilot study. However, we aim to include 20 patients in order to gain as much experience with the intervention as possible, before we decide on conducting an RCT on this subject.

5. TREATMENT OF SUBJECTS

a. Investigational product/treatment

See table 1 in section 3.

b. Use of co-intervention (if applicable)

Study subjects continue using their usual medication.

If medication is adjusted or added by the ADD team, this is noted in the case report form.

6. METHODS

c. Study parameters/endpoints

i. Main feasibility criteria:

75% of included patients complete the intervention.

ii. Secondary study parameters/endpoints

- 1. Description of components and practical aspects of ADD.
- 2. semi-structured interviews with patients and carers to evaluate ADD after six weeks.

d. Study procedures

Baseline	Completion of programme	
CRQ	CRQ	
NRS carer distress	NRS carer distress	
	Semi-structured interview with patient and informal caregiver regarding	
	intervention	
	Structured interviews with the ADD team regarding the intervention	

e. Withdrawal of individual subjects

Subjects can leave the study at any time for any reason if they wish to do so without any consequences.

i. Specific criteria for withdrawal (if applicable)

Hospitalisation for COPD exacerbation during study period. An acute exacerbation during the study period, will lead to exclusion with the possibility to re-enter after stabilization. In that case, patients will follow the same study procedures again.

f. Replacement of individual subjects after withdrawal

After withdrawal, a new subject will be included in the study.

g. Follow-up of subjects withdrawn from treatment

Withdrawal will be recorded in the case record form. Patients will be approached to re-enter the study after stabilisation in case of COPD exacerbation. In that case, they re-start the programme.

082019 15 of 22

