7. STATISTICAL ANALYSIS

Main study parameter/endpoint

Feasibility of ADD: 75% of included patients complete the intervention.

Other endpoints are descriptive.

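### The replacement rules conflict, and nothing says that replaced or re-entering patients stay in the denominator of the 75% completion criterion, so the primary rate can be biased upward

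*Protocol*

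**What the plan says.** Section 7 of the protocol gives the primary endpoint as "Feasibility of ADD: 75% of included patients complete the intervention". Sections 2, 3 and 6c state the same criterion. Section 4 sets the size: "Number of subjects: 20".

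Replacement is described in two places.

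- **Section 2 (primary objective):** "Patients who quit the intervention because of a COPD exacerbation are replaced by another participant". The sentence then turns to other causes: "however patients may drop out of the intervention for different reasons: because they do not want extra hospital visits", followed by finding the intervention unhelpful, family circumstances and other medical complaints. This is part of the explanation of why a completion rate above 75% was thought unrealistic.
- **Section 6f:** "After withdrawal, a new subject will be included in the study", with no condition on the reason. Section 6e, just before it, states: "Subjects can leave the study at any time for any reason if they wish to do so without any consequences".

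On exacerbations, section 6e says: "An acute exacerbation during the study period, will lead to exclusion with the possibility to re-enter after stabilization". Section 4 has the same rule in its list of exclusion criteria, although it describes an event after inclusion. Section 6g adds that withdrawals are recorded in the case record form and that patients who withdrew for an exacerbation are invited to restart.

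**The concern.** A completion rate is only as sound as its denominator. Replacement is harmless if the replaced patient remains counted, and it biases the rate upward if the newcomer takes that patient's place. The protocol does not say which applies. It gives two replacement rules of different scope, and it calls one group of non-completers excluded, which suggests removal.

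Re-entry adds a second gap. A patient who stops for an exacerbation, is replaced, then returns and completes could be scored as a success, a failure, or one of each.

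Completion is the one numeric test of feasibility, and all other endpoints are descriptive. The result feeds the decision on a phase III trial. Two analysts with the same 20-patient data set could reach opposite conclusions, each following the text.

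**Working it through.** **Inputs from the protocol.** Planned number 20 and criterion 75% (sections 4 and 7), so the bar is 0.75 × 20 = 15 completers.

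**Inputs assumed.** The protocol gives no completion rate and no exacerbation rate for this intervention. A true completion of 60% is used for illustration because section 4 quotes a 40% attrition allowance from the cited randomised trial. The split of that 40% between exacerbation (e) and other reasons (o) is varied.

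**The plan's own figures.** There is no calculation behind the 75% criterion to reproduce. The sample-size background does reproduce: 2 × ((1.96 + 0.84)/0.70)² ≈ 32, or 33 per group after rounding up (34 with the t-test version); 66/0.60 = 110; 10% of 110 = 11. This point does not affect it.

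**Step 1. Twenty patients, no replacement.** With X ~ Binomial(20, p), P(X ≥ 15) is:

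| True completion p | 50% | 60% | 70% | 75% | 80% |
|---|---|---|---|---|---|
| P(at least 15 of 20) | 0.021 | 0.126 | 0.416 | 0.617 | 0.804 |

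**Step 2. Section 2 rule, replaced patients dropped.** The apparent rate is c/(1 − e), where c = 1 − e − o is true completion.

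| e | o | True c | Apparent rate | P without replacement | P with replacement and removal |
|---|---|---|---|---|---|
| 10% | 30% | 60% | 0.60/0.90 = 66.7% | 0.126 | 0.297 |
| 20% | 20% | 60% | 0.60/0.80 = 75.0% | 0.126 | 0.617 |
| 30% | 10% | 60% | 0.60/0.70 = 85.7% | 0.126 | 0.945 |
| 10% | 20% | 70% | 0.70/0.90 = 77.8% | 0.416 | 0.726 |

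The rate is inflated in every row, but the criterion can still fail.

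**Step 3. Section 6f rule, every non-completer treated as withdrawn and dropped.** Recruitment continues until 20 complete, so the result is 20/20 whatever the true rate. The expected number of starters is 20/p: about 33 at 60% and 40 at 50%.

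**Step 4. Replaced patients kept.** With 20 completers and w replaced, the rate is 20/(20 + w):

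- w = 6: 20/26 = 76.9%, criterion met
- w = 7: 20/27 = 74.1%, not met
- w = 10: 20/30 = 66.7%, not met

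All three read 20/20 = 100% if the replaced patients are dropped. Under the section 2 rule, 5 other drop-outs and 4 replaced exacerbations give 15/20 = 75% when the 4 are dropped and 15/24 = 62.5% when they are kept. The same events pass or fail according to a counting rule that the protocol does not state.

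**The case against.** The strongest reply is that the protocol never removes anyone. A patient who consented, started and stopped was included, and section 6f only adds a newcomer. On that literal reading there is no bias. It is a fair reading, but it is nowhere stated, and describing exacerbation patients as excluded points the other way.

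A second reply is that section 6f follows the exacerbation criterion in 6e and may cover only that case, in line with section 2. That is possible. However, 6g names exacerbation when it means only those patients, and 6f does not.

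A third reply is that setting exacerbations aside is an openly declared, narrower target, and that the recorded withdrawals would let the full rate be recovered. This stands in part: the narrower rate is legitimate if it is labelled as such and the counts are reported.

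Three stronger inferences are tempting, and the documents do not support them:

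- **The criterion is met by construction.** This holds only if 6f covers every withdrawal and the replaced patients are dropped. That reading conflicts with section 2, where drop-out for other reasons is the reason for not expecting more than 75%.
- **Exacerbation is a main cause of non-completion here.** The protocol gives no rates by reason.
- **The phase III trial would be undersized.** Assuming 25% attrition instead of 40% would give 68/0.75 ≈ 91 rather than 68/0.60 ≈ 114 patients. But section 4 says that the future calculation would be comparable to the cited trial's, which allowed 40%. Nothing says that the pilot rate would set attrition.

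A statistical analysis plan could define the denominator. It could not settle which patients are replaced during recruitment, and the conflict lies in the protocol's own text.

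**Conclusion.** The point holds in a limited form. Sections 2 and 6f differ in scope as written, sections 4 and 6e exclude patients after inclusion and allow re-entry, and no section says how replaced or re-entering patients count. The primary completion rate can therefore be biased upward; the protocol does not establish that it will be.

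The size depends on an unstated counting rule and on assumed rates. If replaced patients are dropped under the section 2 rule, 60% true completion reads as 67% to 86% for an exacerbation share of 10% to 30% of patients, and the chance of reaching 15 of 20 rises from 0.13 to between 0.30 and 0.95. At a 20% share it reads as 75%, with a chance of 0.62. If replaced patients are kept, that inflation disappears, and more than 6 replacements for 20 completers miss the criterion. The gap should be closed because it concerns the study's only numeric success criterion and costs almost nothing to close.

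**What to change.** 1. Reconcile the wording on replacement and exclusion in sections 2, 4 and 6e to 6g so that one rule applies throughout. This includes whether hospitalisation for an exacerbation or any acute exacerbation triggers withdrawal, since section 6e uses both. Which clinical rule applies is for the investigators to decide.
2. State in sections 2, 6 and 7 that the primary denominator is every patient who signed consent and was included, each counted once. Replacements may be recruited to gain experience, but they add to the denominator and never substitute.
3. State in advance how a patient who re-enters after an exacerbation is scored: one patient, one outcome.
4. Report the number ever included and withdrawals by reason. Give the completion rate excluding exacerbation withdrawals only as a secondary figure.

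The cost is a wording amendment, which section 10.2 requires to go to the ethics committee. It needs no extra patients or visits, and the withdrawals are already recorded. The downside is that the reported completion rate may be less favourable.
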